10.1 Quantitative Sensory Testing (QST)

Participants will complete a multimodal QST battery to characterize sensory function. Participant instructions are scripted, and all participants will undergo familiarization training for each procedure prior to data collection to reduce QST-related anxiety and measurement noise. All procedures can be stopped at any time by participant request if they become unbearable.

Pressure pain sensitivity will be assessed using an algometer with a 1-cm² rubber probe (FPK20, Wagner Instruments, Greenwich, CT, USA; or Algometer Type II, SBMedic, Solna, Sweden) to quantify pressure pain thresholds (PPT). The primary or “index” testing site will be located at the lower back by the participant’s response to manual over-pressure (springing palpation). A control or “remote” site will be located over the contralateral trapezius or deltoid muscle (diagonal from lower back site). Multisite pain hypersensitivity, particularly at asymptomatic remote sites, is a core feature of centralized pain.^{86,87} Pressure will be manually increased at a rate of 0.5 kgf/cm²/s (10 kgf max, metronome guided as required) until participants first indicate that the sensation pressure becomes one of faint pain. Pressure intensity (in kgf) at that time will be recorded as the PPT. Measurements will be conducted 3x/site (separated by 20 – 60-s rest intervals) with means used for analysis. Probe placement will be varied slightly trial to trial to prevent tissue sensitization from repeated testing of the same site. Additionally, we will use the Multimodal Automated Sensory Testing (MAST) System (Arbor Medical Innovations, LLC, Ann Arbor, MI, USA)⁸⁸⁻⁹¹ to apply computer-controlled pressure at the thumbnail bed to derive a suprathreshold measure of pressure intensity that evokes a moderate level of pain (i.e., Pain50) as well as pain tolerance. We have extensive experience using thumbnail pressure as an evoked pain stimulus and its validity in the measurement of centralized pain has been demonstrated extensively.⁹²⁻¹⁰⁴ The system delivers an ascending series of discrete pressures (5-s duration; 4 kgf/cm²/s ramp rate) at 20-s intervals, beginning at 0.25 -.50 kgf/cm² and increasing in 0.25 - 0.50 kgf/cm² steps. Pain intensity will be rated after each stimulus on a 0-10 or 1-100 NRS. The test will be terminated when participants reach their tolerance or 10 kgf/cm². Lastly, large volume, deep muscle pressure sensitivity^{105,106} will be assessed using a MRI-compatible rapid cuff inflator (Hokanson, Bellevue, WA, USA).¹⁰⁷⁻¹⁰⁹ This system includes an air compressor, computerized pressure controller, and a 13.5 cm X 82.5 cm velcro-adjusted pressure cuff. Participants will first receive an ascending series of cuff pressures, starting at 20-60 mmHG and increasing in 10-20 mmHG steps (5-10-s pressures, 10-20-s rest intervals) to tolerance or to a maximum of 400 mmHG. Each pressure will be rated after deflation on a 0-10 or 0-100 NRS. These pain ratings will be used to interpolate a series of 8 tolerable cuff pressures that will delivered in pseudo-randomized order and rated individually on pain intensity and unpleasantness. Stimulus response curves will be constructed for each participant and used for analysis, along with several derived variables: *cuff-PPT*, *cuff-Pain50*, and *cuff-Tolerance*. In addition, tonic pain induced by continuous cuff pressure will be assessed (*tonic-Cuff*). Each participant’s individually calibrated Pain40-60 pressure (i.e., pressure that evokes a 40-60/100 pain rating) will be applied for 6-min to one gastrocnemius muscle. Pain intensity and unpleasantness ratings will be obtained every 60-s.

Conditioned pain modulation (CPM) procedures require a conditioning stimulus to induce endogenous analgesic systems and alter pain perception, and a test-stimulus to evaluate the endogenous analgesic response to the conditioning stimulus. CPM is attenuated in the majority of chronic pain participants and its magnitude is predictive of a variety of pain outcomes.¹¹⁰⁻¹¹² As in our previous studies, painful pressure delivered to one thumbnail by the MAST System will serve as the test stimulus; non-painful “touch” pressure (0.25 kgf/cm²) or moderately painful pressure delivered to the contralateral thumb will serve as a neutral and a painful conditioning stimuli, respectively.¹¹³⁻¹¹⁵ CPM magnitude will be calculated as the difference in pain ratings to the test stimulus applied prior to and during the conditioning stimuli, with reductions in test stimulus ratings during painful conditioning interpreted as evidence of intact endogenous pain inhibition. An alternative CPM procedure may be conducted instead using cold stimulation, consistent with the method of Locke¹¹⁶ and others.^{117,118} In this procedure, immersion of one hand into a circulating cold water bath (6-12°C; NESLAB Digital One RTE 7, Thermo Scientific, Newington, NH, USA or similar) will serve as the conditioning-stimulus and PPT at the lower back, trapezius or deltoid will serve as the test-stimulus. Baseline ratings of the test-stimulus will be acquired during the assessment of pressure pain sensitivity (see above). Conditioning stimulation will begin by immersing the hand to a level 10 cm above the wrist into the water bath. The hand will be immersed for 60 – 90-s (or to each participant’s individual tolerance but not longer than 90-s); perceived pain of the water will be rated several times during hand immersion and at the time of hand withdrawal, using a 0-10 or 0-100 NRS, to determine the adequacy of conditioning pain.¹¹⁹ After 30 – 60-s of hand immersion, lower back, trapezius or deltoid PPT will re-measured 2-3 times while the hand is still immersed in the cold

water or after it has been withdrawn. CPM magnitude will be calculated as the difference in mean PPT measured prior to and during the conditioning stimulus, with increases in PPT during conditioning interpreted as evidence of efficient endogenous pain inhibition.

Temporal Summation measures increases in excitatory pain pathways and is thought to reflect the progressive increase in dorsal horn neuronal firing in response to repetitive C-fiber stimulation.¹²⁰⁻¹²³ Enhanced temporal summation is common in chronic pain and is predictive of pain outcomes.^{124,125} We will evaluate temporal summation in triplicate using either a 256 mN pinprick (MRC Systems GmbH, Heidelberg, Germany), a 40 g Neuropen (Owen Mumford, Oxfordshire, United Kingdom), or a 300 g nylon monofilament applied to the lower back, as well as to the trapezius or the deltoid and/or the forearm, followed by a train of 10 identical stimuli (1 Hz). Following the single stimulus and the train of 10 stimuli, participants will report the pain intensity of the pinprick sensation using a 0-10 or 0-100 NRS. Temporal summation for each site will be calculated as the mean difference in pain ratings evoked by the single stimuli and the trains of stimuli. The degree of lingering pain evoked by this procedure, referred to as *pain aftersensations*, will also be recorded for up to 90-s following the last set of stimuli at each site.

Michigan Visual Aversion Stress Test (M-VAST) will probe mechanisms of sensory sensitivity that bypass somatic peripheral receptors and the spinal cord, and are amplified in many chronic pain participants.^{92,126-128} Participants will be presented with a flashing annular checkerboard pattern at varying illumination levels as performed previously.¹²⁹ Participants will be acclimated to a dark room and exposed to a high resolution, calibrated LED monitor displaying the visual stimulus. Each visual stimulus intensity level and the entire task will be rated on both sensory intensity and unpleasantness scales. These rating will be used to compute stimulus-response curves for analysis.

[figure not shown]
Two Point Discrimination Prior studies in participants with cLBP have documented subtle limitations in mechanical somatosensory sensitivity¹³⁰⁻¹³² and these are important to measure in a study of central nervous system processing of pain. Therefore, in addition to studying mechanical pain sensitivity, we will assess two-point discrimination thresholds, a measure of tactile acuity for non-painful mechanical sensation. As in previous studies, we will use a two-point aesthesiometer (BASELINE Evaluation Instruments, White Plains, NY, USA), applied to the lower back and to a (non-painful) control site on the upper limbs. Participants will complete series of ascending (in which the 2 points of the aesthesiometer are initially adjacent) and descending (in which the 2 points of the aesthesiometer are initially far apart) trials in which they indicate whether they "feel one or two points" when the stimulus is applied. The distance between the points is then either increased or decreased until the experimenter locates the minimum distance at which the participant perceives 2 points instead of one. The results of ascending and descending trials are averaged to calculate the two-point discrimination threshold. These procedures are commonly used in the practice of clinical neurology, are non-invasive and non-painful, and are not associated with any known risk.

QST Feasibility and Anticipated Results These procedures engage different aspects of pain perception and potentially different peripheral and central mechanisms, thus permitting a comprehensive investigation into the psychophysical characteristics of cLBP. This testing strategy has been extensively employed and validated by our group and multisite networks, including the NIDDK MAPP^{90,133} and LURN^{133,134} Networks, and the German Neuropathic Pain Network.¹³⁵ We anticipate no significant issues with implementation. As stated above, we hypothesize that cLBP participants with lower pain sensitivity at the thumbnail (i.e., higher pain thresholds) will respond to acupressure,^{136,137} whereas those with diminished CPM will be more likely to respond to duloxetine.¹³⁸ We further hypothesize that participants with multiple indices of centralized pain, including generalized pain hypersensitivity (i.e., increased pressure pain sensitivity at the lower back and multiple remote body sites), facilitated temporal summation, and visual hypersensitivity, will preferentially respond to centrally-acting treatments. Lastly, participants with localized pain hypersensitivity at the lower back, but not at other body areas, will show preferential response to interventional procedures.

10.2 Magnetic Resonance Imaging

All participants will also undergo spinal MRI to assess structural abnormalities of lower back (see Section 6.6 for imaging on all participants). Additionally, a subset of participants enrolled in the deep phenotyping study will undergo four different brain neuroimaging procedures (Figure 10): 1) functional connectivity MRI (fcMRI) at rest, 2) proton magnetic resonance spectroscopy (¹H-MRS) of the posterior insula assessing combined glutamate and glutamine (Glx), 3) evoked pressure pain at a neutral site, and 4) voxel based morphometry to assess gray matter volume in S1 and primary motor (M1) cortex. Following physical maneuvers to exacerbate clinical pain, resting state fcMRI and ¹H-MRS scans will be repeated to assess the neurobiological response to increases in pain, as we have previously demonstrated in FM using pressure.¹³⁹ The methods described below have been successfully employed previously by our group, and probe different aspects of the brain's involvement in pain processing, thus complementing our QST methods by providing a comprehensive neurobiological signature of cLBP. Familiarization procedures will be completed prior to MRI to reduce anxiety. Neuroimaging will require approximately 90 minutes to complete. MRI will be done on a 3 Tesla scanner either at the Functional MRI Lab on UM North Campus (GE scanner) or in the Department of Radiology at the UM

Figure 10 Deep Phenotyping fMRI Breakdown

Main Hospital (Philips scanner).

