10.2.2 Proton Magnetic Resonance Spectroscopy (1H-MRS)

During ¹H-MRS, quantifiable measures of brain metabolites will be acquired from multiple brain regions non-invasively. The metabolite we will focus on is glutamate, the brain's major excitatory neurotransmitter. Previous ¹H-MRS studies, performed by our group, have examined changes in Glx (combined glutamate and glutamine) in cross sectional participant-control^{103,136,168,169} and longitudinal treatment studies.^{104,143} We find that FM participants display elevated Glx within the posterior insula and this concentration is reduced following active treatment, and this reduction was correlated with a reduction in clinical pain.¹⁴³ We have also shown that pelvic pain participants have elevated Glx within the anterior insula which is in turn associated with increased connectivity to the medial prefrontal cortex, a DMN structure.¹⁷⁰

Data Acquisition: ¹H-MRS will be performed as in our previously published studies.^{103,143,170} In brief, we will examine Glx within the posterior insula twice (before and after back pain maneuvers). Our primary ¹H-MRS outcome will be baseline Glx within the posterior insula. ¹H-MRS studies are performed on the same magnet as fMRI. PRESS (TR/TE=2000/35 ms) single voxel ¹H-MRS is performed on the region of interest with voxel sizes of 2x2x3 cm. The water signal is recorded using 8 averages. Standardized voxel placements are guided by visual inspection of anatomical T1-weighted images as reported previously.¹⁰³

Preprocessing: Raw data from each single-voxel MR spectroscopy sequence will undergo manual post-processing using ¹H-MRS software (LCModel; Stephen Provencher, Oakville, Ontario, Canada). LCModel uses a linear combination of individual spectra obtained from pure molecular species to fit the experimental spectra.¹⁷¹ Glx values will be calculated both as an absolute concentration using the water signal for normalization and as a ratio to creatine. Glx absolute concentrations will be reported in arbitrary institutional units. Correction for cerebral spinal fluid (CSF) volume, which can dilute ¹H-MRS-derived Glx values, will be performed as reported previously.¹⁰³ Metabolite concentrations will be excluded if the Cramér-Rao bounds are greater than 20%.

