Group Level Analysis: CSF-corrected Glx values will be entered into a multiple regression model in SPSS with change in pain (post minus pre-treatment) as the dependent variable and Glx values as a covariate of interest. Age and sex will be entered as nuisance regressors.

10.2.3 fMRI of Evoked Cuff Gastrocnemius Pain

Whole brain blood oxygen level-dependent (BOLD) functional images will be acquired using the same 3 Tesla scanner and T2*-weighted EPI multiband sequence as described for the resting state scan. Each participant will undergo a 11-minute block design scan, during which 6 cuff pressures (equal pressure = 15-30 and 100-115 mmHg; equal pain = 40-60/100 numerical rating scale (NRS) units will be applied to the left calf using the pressure cuff device (described in Section 10.1) in pseudo-random order. Pain levels for each participant will be determined during the QST assessment. Each pressure stimulus will be applied for 14 seconds. Prior to each pressure stimulus, a 4-second visual cue will be presented to signal upcoming cuff pressure to limit any stimulus-onset startle reflex. Participants' head motion will be minimized using foam pads around the head, and a strap secured across the forehead.

Pre-processing: Same as resting state fcMRI. See Section 10.2.1.

Group level analysis: The activation maps (pain minus rest) will be entered into a GLM to determine the neurobiological correlates of evoked pain that best predict treatment response (change in pain as the dependent variable). In addition, SVM will be implemented to create a machine learning model for prediction and discrimination between responder and non-responder (see corresponding Section 10.2.1). Resulting maps are thresholded at $p < .001$ uncorrected voxel threshold with $p \leq .05$ FDR significance corrected for multiple comparisons.

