10.2.4 Brain structural Imaging with Voxel Based Morphometry (VBM)

We have published extensively using VBM methods in various chronic pain states.¹⁷⁸⁻¹⁸¹ In brief, our protocol includes T1-weighted structural images (TR 2400/TE 2.14ms; Flip angle 8 deg; FOV 224X224; Voxel size 0.8mm isotropic) segmented into white matter (WM), gray matter (GM), and cerebral spinal fluid using the

segment function in SPM12, running under MATLAB 2017a. The resulting GM segments are then processed using the diffeomorphic anatomical registration through exponentiated lie algebra (DARTEL) toolbox.¹⁸² We will normalize VBM data to standard space. We will smooth normalized, modulated images with a Gaussian kernel, and pass individual participant maps up to group level analysis.

Group Level Analyses: We will enter smoothed GM images into a multiple regression model in SPM12 with change in pain interference (post minus pre-treatment) as the covariate of interest. Age and total brain volume will be entered as nuisance regressors. We will exclude voxels with GM values < .1 from analysis.

Feasibility: We anticipate few problems in data analysis based on our past studies.^{154,178-181}

Feasibility and Anticipated Neuroimaging Results. We have published extensively in the field of fcMRI, evoked pain fMRI, and ¹H-MRS, and expect no issues with data acquisition or analyses.^{102-104,115,129,136,142-144,146,155,156,168,183-186}

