10.3 Biospecimen Collection for Inflammation Methods

No more than 10mL of blood will be collected at each deep phenotyping visit. All samples will be stored initially at the University of Michigan but may be sent to other MRCs or central biorepositories for future storage or additional analyses.

Stimulated Assays. The TruCulture system (Myriad RBM) consists of small vacutainers preloaded with immune stimulants (e.g., LPS) or control media into which whole blood is drawn. Following incubation in a small table-top unit, the supernatant is isolated without the need for centrifugation using a small plunger included in the kit. Whole blood is drawn via venipuncture into two different 1 mL tubes containing lipopolysaccharide (LPS; 100 ng/mL), or media (NULL). LPS is potent agonist of TLR4.¹⁸⁷ Samples are immediately incubated at 37° C for 24 hours, after which the supernatant is isolated with a valve separator included in the kit. The supernatant is frozen at -80° C prior to shipment to a biorepository where it is thawed, aliquoted into 0.25 mL containers, and stored at -80° C for batch analysis. All batches include control standards (i.e., samples provided by lab personnel) to allow for estimation of batch effects.

Cytokine/Chemokines are analyzed from supernatant using multiplex Luminex xMap technology or equivalent. We have completed a series of dilution protocols to determine optimal concentrations to keep each analyte in the dynamic range of the assays. A minimum of seven cytokines/chemokines will be analyzed from each sample including those in the pro-inflammatory NF-κB- mediated suite (IL-1β, IL-6, TNF-α), chemotactic cytokines (IL-8, MCP-1, MIP1α), and regulatory cytokine IL-10.

Analyses: Cytokine/chemokine data often does not follow a normal distribution, which can create issues when using parametric statistical approaches. Therefore, we will evaluate normality with the Shapiro-Wilk test statistic and apply Box-Cox transformations where required. Any values below the lower limit of detection will be set to half that value. Multi-level models will be employed that can accommodate random effects for each batch analysis (in case significant variation is observed between-batches), and for site of collection.

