Imaging data will be obtained using one of two 3.0 T GE MRI scanners located at the Functional Magnetic Resonance Imaging lab at University of Michigan or at the University Hospital 3.0 T Philips scanner. The two GE scanners are completely dedicated for research and have identical operating systems and pulse sequences allowing for flexibility in scheduling. Imaging data will be de-identified and stored on secure, password-protected HITS servers. All analyses will be performed at the CPFRC.

Participants will also be asked to provide blood samples. All blood samples will be de-identified prior to storage. All samples will be collected, securely stored, and processed for disbursement and analysis by appropriate study investigators. Participant identity and confidentiality will be maintained throughout.

17 Data, Sample Storage and Sharing

Study data, biospecimens and neurobiological data will be stored securely at the Back & Pain Center or the CPFRC in Domino Farms at the University of Michigan or at sites NIH selects for this study. Data and samples will be stored indefinitely. Participant names and other personally-identifying information will not be kept with the data or samples. Data and samples will either be stored without a code linking them to the subject or they will have a code that links to identifying information. If data has a code, the key to the code will be kept at Back & Pain Center, the CPFRC at the University of Michigan or electronically to be used for patient tracking. This code will be kept in a separate, secure area and will not be shared outside of University of Michigan.

Accelerometer/EMA data from the PRO-Diary, AcuWand data and MBSR recordings all will be stored and shared internally via Dropbox, which is Michigan's HIPAA compliant cloud storage and collaboration service. It is capable of handling PHI and other sensitive data (e.g., research data). After it is cleaned and scored, the PRO-Diary data will be later merged with the REDCap data prior to analysis.

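### Deep-phenotyping brain scans may come from GE or Philips magnets, and no stated model accounts for scanner; any remaining vendor offset would attenuate the eight MRI and 1H-MRS modifiers

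*Protocol*

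**What the plan says.** **Scanners.** Protocol section 10.2 gives a choice of magnet for the brain imaging: "MRI will be done on a 3 Tesla scanner either at the Functional MRI Lab on UM North Campus (GE scanner"), or a Philips magnet at the main hospital. Section 16 (Data Management) repeats the choice, ending "or at the University Hospital 3.0 T Philips scanner". Section 10.2.2 puts spectroscopy on the same magnet as the fMRI, so it has the same vendor mix. The only statement on equivalence is in section 16: "The two GE scanners are completely dedicated for research and have identical operating systems and pulse sequences". It does not extend to the Philips.

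**Glx.** Section 10.2.2 says "Glx absolute concentrations will be reported in arbitrary institutional units", and also "Glx values will be calculated both as an absolute concentration using the water signal for normalization and as a ratio to creatine". A CSF correction is applied. The group model does not say which of the two scales it uses.

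**Covariates in the imaging models.**
- Connectivity (10.2.1): age and sex. The hub and SVM analyses list none.
- 1H-MRS (10.2.2): "Age and sex will be entered as nuisance regressors".
- Evoked-pain fMRI (10.2.3): none listed.
- VBM (10.2.4): "Age and total brain volume will be entered as nuisance regressors".
- SAP 9.1.2: takes its form from 9.1.1, whose covariates are sex, age, BMI, race, education and the T2 score.

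**Contrast within the plan.** For cytokines, Protocol section 10.3 does plan for this kind of nuisance variation: "Multi-level models will be employed that can accommodate random effects for each batch analysis", and for collection site.

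**The concern.** A moderator analysis compares people with one another on the level of the imaging measure. If two vendors give different levels for the same biology, part of the spread in the predictor is machine rather than phenotype, and the estimated moderation shrinks. Eight of the 15 rows in SAP Tables 3 and 5 depend on these scanners: four regional fMRI activities, three connectivity measures and posterior insula glutamate. Much of the Aim 3 predictor analysis therefore rests on them.

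The exploratory pre-post analyses (Protocol 10.2.1 and 18.2.2) use paired t-tests. An additive offset cancels in a paired change only when both visits use the same vendor, and no rule requires that.

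**Working it through.** **1. The plan's own figure.** SAP 6.1 states 80% power for r=0.42 with n=40, two-sided 5%. By Fisher z: atanh(0.42) × √37 = 0.448 × 6.083 = 2.723; power = Φ(2.723 − 1.960) = 77.7%. Simulating the t-test of the correlation gives 78.7%. The Protocol's version (r=0.43, 81%) gives 79.9% and 81.0%. The stated figures are essentially reproduced. The Fisher z value, 77.7%, is the base below.

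**2. Attenuation in a single arm.** Let p be the Philips share and d the vendor offset in within-scanner SDs. Both are assumptions. If scanner is unrelated to outcome, the predictor variance grows by the factor 1 + p(1−p)d², so r_obs = r / √(1 + p(1−p)d²).

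| p | d | 1 + p(1−p)d² | r_obs | Power, n=40 |
|---|---|---|---|---|
| any | 0 | 1 | 0.420 | 77.7% |
| 0.10 | 0.25 | 1.006 | 0.419 | 77.5% |
| 0.30 | 0.5 | 1.0525 | 0.409 | 75.3% |
| 0.30 | 1 | 1.21 | 0.382 | 68.7% |
| 0.50 | 1 | 1.25 | 0.376 | 67.1% |

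In a single-slope model, a scanner covariate costs one degree of freedom and holds power at about 76.6% whatever the offset.

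**3. The SAP 9.1.2 interaction.** Here the target is treatment × phenotype. Write the measured predictor as Z = Z* + dS, with S the scanner indicator. Then A·Z = A·Z* + d·A·S. The unwanted part is a treatment-by-scanner term, which a scanner main effect cannot absorb. The expected shrinkage of the unadjusted slope is 1 / (1 + p(1−p)d²) = 1/1.21 = 83% for p=0.3, d=1. A simulation with four arms of 40, one of them moderated at r=0.42, agrees:
- Unadjusted: about 83% of the true interaction.
- Scanner main effect added: about 83%, so nothing is recovered.
- Treatment-by-scanner terms, or standardising the predictor within scanner: about 99–101%.

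**4. False association.** With no true association, suppose outcome differs by g SD between scanners. The spurious correlation is p(1−p)dg / √[(1 + p(1−p)d²)(1 + p(1−p)g²)]. For p=0.5, d=1, g=0.5 this is 0.125 / √(1.25 × 1.0625) = 0.108. A nominal 5% test then rejects in about 10% of trials at n=40 and 28% at n=160. With g=0 it is zero.

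**The case against.** Several points on the other side stand.

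- **The Philips may be little more than a back-up.** Protocol 3.2 and SAP 5.2 speak of one off-site imaging location, and Protocol section 16 links scheduling flexibility to the two GE magnets. If the Philips share is near zero, so is the effect.
- **Glx is not raw signal.** A reader might infer from the arbitrary units alone that Glx levels depend on the machine. The unit label does not establish that. Absolute Glx is water-referenced and CSF-corrected, and a creatine ratio is also computed. These steps may shrink an offset, though nothing shows that they remove it, and they do not apply to the seven fMRI modifiers.
- **One additive offset is a simplification.** Evoked activation is a pain-minus-rest contrast within a session, and connectivity is a correlation, in which a constant gain difference cancels. The size of any remaining offset may differ by measure.
- **False moderators are not the default outcome.** A reader might infer that drift in scanner use over calendar time is enough to create them. It is not: drift alone only attenuates. A false association needs scanner use to track outcome as well, and a false moderator needs that relation to differ between randomised arms.
- **Large losses are not documented.** With p=0.3 and d=2 the same formula gives about 50% power, but nothing in the documents supports an offset that large.
- **Scope.** The primary endpoint is untouched, Protocol 18.1 labels the mechanistic analyses exploratory, and SAP 9.1.2 is a second analysis.

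None of this supplies a scanner term, a harmonisation step or a same-vendor rule.

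**Conclusion.** The gap is real, and its size is conditional. Two vendors are permitted, equivalence is claimed for only one, and no stated group-level or SAP deep-phenotyping model accounts for scanner. If a material share is scanned on Philips and an offset survives water-referencing and CSF correction (Glx) or the within-session contrast (evoked fMRI), the eight MRI and 1H-MRS modifiers are attenuated. At 30% Philips the cost is about 2 points of single-arm power for a 0.5 SD offset and about 9 points for 1 SD. Share and offset are both assumed, so the documents do not support saying that vendor offsets will be read as phenotype, only that the plan does not prevent it. The point should be fixed because the remedy is cheap, and because the obvious remedy, a scanner main effect, fails in the SAP model.

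**What to change.** - Record the scanner for every deep-phenotyping session.
- In SAP 9.1.2, standardise each imaging predictor within scanner vendor, or add treatment-by-scanner terms. Do not rely on a scanner main effect alone. Standardising presumes that participants are not steered to a vendor by phenotype, so state how scanners are assigned.
- Add scanner as a covariate in the single-slope connectivity, 1H-MRS, evoked-fMRI and VBM group models.
- Keep Deep Visits 1 and 2 of a participant on the same vendor, and exclude vendor-switched pairs from the paired t-tests.
- Name the Glx scale used in the main model, and report Glx/creatine as a sensitivity measure.

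The cost is a few degrees of freedom, any vendor-switched pairs lost from the paired tests, and slightly less scheduling flexibility. If all deep-phenotyping brain scans are done on the GE magnets, a sentence to that effect is enough.
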